4.15. Prohibited Procedures and Treatments

Subjects who undergo a subsequent surgery involving the initial TKA incision within 90 days must withdraw from the study.

Subjects who receive a subsequent TKA revision on the same knee within 90 days of the study revision must withdraw from the study prior to the procedure. Sites will record any SSCs that occur prior to the subsequent TKA revision and document the revision as the reason for the withdrawal from the study.

In the absence of an SSC, subjects receiving cross-over therapy after completing the original study treatment (ie, therapy from the arm in which the subject was not initially treated) must withdraw from the study.

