2.1 Sample Size and Power

The primary endpoint of this study is the subject incidence of SSC. The incidence rates of SSC are different for septic and aseptic revisions; the assumed SSC rate is 33% for septic and 6.9% for aseptic. This study plans to enroll at least 50% septic revisions overall. These enrollment rates lead to an assumed pooled SSC rate of 20% in the SOC dressing arm.

Assuming an overall type 1 error rate of 0.05, with a two-sided hypothesis test, the study will have at least 80% power to detect a difference of 10% (50% reduction) in SSCs in the ciNPT arm with 199 subjects in each treatment arm, with one interim analysis at about 50% of the evaluable subjects for a total of 398

subjects using the likelihood ratio test. With an estimated 5%-10% loss, a non-binding interim analysis for superiority at approximately 50% of the evaluable subjects using O'Brien-Fleming method for monitoring boundaries, the planned sample size will be inflated for a potential loss of follow-up for a total of 440 subjects.

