The first test will utilize all subjects from the mITT combined population included in the interim and subjects post-interim. The second test will utilize only the post-interim mITT subjects from either the septic or aseptic population depending on the results and/or decision from the interim analysis. The second test will be performed only if the test 1 is statistically significant at the 0.048 level.

Case 1 Did Not Enrich	Case 2 Enriched with Septic	Case 3 Enriched with Aseptic

 • Test 1: Adaptive test of H_0 (Combined population) 	
 • Test 1: Adaptive test of H_0 (Combined population) • Test 2: standard test of H_0 (post-interim population only) 	
 • Test 1: Adaptive test of H_0 (Combined population) • Test 2: standard test of H_0 (post-interim population only)

For Case 1, if the 2-sided p-value from the test 1 is ≤ 0.048 and the SSC rate of the ciNPT arm is lower than the SSC rate of SOC arm, then the null hypothesis is rejected; superiority in effectiveness of the ciNPT arm compared with the SOC arm will be established. However, for Case 2 or Case 3, both test 1 and test 2 must reject the null hypothesis at the 0.048 level in order to claim statistical significance.

Additionally, figure(s) may be generated to display the results from the analyses of the primary endpoint graphically.

Supportive/exploratory analyses of the primary efficacy endpoint described below in Section 8.5.1 will be performed on the mITT analysis set unless otherwise specified.

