8.7.1 Pain Analysis

Both worst pain and average pain are measured from 0 (no pain) to 10 (pain as bad as you can imagine). A positive value of change from baseline indicates increased pain post-baseline as compared with baseline; a negative value indicates reduced pain post-baseline as compared with baseline. Both worst pain score and average pain score along with change from baseline will be summarized separately by treatment arm and by visit. Change from baseline for both worst pain score and average pain score will be analyzed separately using a mixed model, which includes (“Treatment Arm” and “Visit”) plus the interaction term (“Treatment Arm by Visit”), revision type, clinical site, and with subject as a random effect. Least squares (LS) means along with 95% confidence intervals and p-values at each post-baseline timepoint will be presented.

If an overall missing data rate for worst or average pain scores is 10% or greater, then an approach of multiple imputation based on Rubin’s [1976, 1987]^{3,4} for missing data will be used by creating several different plausible imputed data sets and appropriately combining results obtained from each of them. A basic description of the multiple imputation includes:

1. Using SAS procedures including Proc MI and Proc MIANALYZE;
2. Using the fully conditional specification (FCS) method / algorithm [Brand 1999 and van Buuren 2007]^{5,6} which is a linear regression for continuous variables;
3. Including treatment arm, age (≥ 65 or < 65 years), sex, BMI (≥ 35 kg/m² or < 35 kg/m²), race/ethnicity, material used in the TKA revision, and co-morbidities in the imputation model;
4. Creating five imputed datasets [Rubin 1996]⁷;
5. Combining completed-data estimates from five imputed datasets.

The mixed model analysis described above will be repeated based on the imputed data.

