The normalized scores and change from baseline for each subscale will be summarized by treatment arm and by visit. Change from baseline for normalized scores for each subscale will be analyzed using a mixed model, which includes fixed effects (“Treatment Arm” and “Visit”) plus the interaction term (“Treatment Arm by Visit”), revision type, clinical site, and with subject as a random effect. LS means along with 95% confidence intervals and p-values at each post-baseline timepoint will be presented.

If a missing data rate for any subscale is 10% or greater, then an approach of multiple imputation based on Rubin’s [1976, 1987]^{3,4} for missing data for all subscales will be used by creating several different plausible imputed data sets and appropriately combining results obtained from each of them.

A basic description of the multiple imputation includes:

1. Using SAS procedures including Proc MI and Proc MIANALYZE;
2. Using the fully conditional specification (FCS) method / algorithm [Brand 1999 and van Buuren 2007]^{5,6} which is a linear regression for continuous variables;
3. Including treatment arm, age (≥ 65 or < 65 years), sex, BMI (≥ 35 kg/m² or < 35 kg/m²), race/ethnicity, material used in the TKA revision, and co-morbidities in the imputation model;
4. Creating five imputed datasets [Rubin 1996]⁷;
5. Combining completed-data estimates from five imputed datasets.

The mixed model analysis for each subscale described above will be repeated based on the imputed data.

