10 CHANGES FROM PLANNED ANALYSIS

All changes made from planned analyses in the study protocol are listed below.

- For the interim analysis, per Section 8.4.5 of the study protocol, it was stated the increase to the final sample size would only occur if the interim results had conditional power of success $\geq 50\%$, would be subject to the restrictions in Chen et al. [2004]², and would not be considered statistically binding. To further clarify, an increase to the final sample size can occur if the conditional power is below 50%. If the sample size is increased when conditional power is $\geq 50\%$, a type I error rate would not be inflated as mentioned in Chen et al. [2004]². If the sample size is increased when conditional power is $< 50\%$, an adjustment will be needed to control the Type I error. The adjustment is outlined in Section 7.3 of the interim SAP.
- Per Section 8.1.3.2 of the study protocol, it was stated: For the subscale scores, four possible outcomes will be summarized and listed: i) Normalized numeric subscale score; ii) Assessment done but incomplete; iii) Discontinued study prior to assessment; iv) Assessment not done. Section 8.7.2 of this final SAP only have two possible outcomes: i) Normalized numeric subscale score calculated based on KOOS Scoring 2012; ii) Missing assessment score for any reason.
- Per Section 8.1.3.3 of the study protocol, it was stated: For each subscale, there are four possible outcomes: i) Raw numeric subscale score and converted t-score; ii) Assessment done but

incomplete; iii) Discontinued study prior to assessment; iv) Assessment not done. Section 8.7.3 of this final SAP will have two possible outcomes: i) Raw numeric subscale score and converted t-score; ii) Missing assessment score by any reason.

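### For KOOS and PROMIS, the planned imputation shares the mixed model's missing-at-random assumption and omits SSC and re-operation, so it cannot expose bias from subjects withdrawn for further surgery

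*SAP*

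**What the plan says.** SAP 8.7.2 (KOOS) and 8.7.3 (PROMIS) analyse change from baseline with a mixed model: arm, visit, their interaction, revision type, site and a random subject effect. SSC status is not a term.

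SAP 7.3 calls the multiple imputation of these scores a sensitivity analysis and names no other method for them. The rule in SAP 8.7.2 begins "If a missing data rate for any subscale is 10% or greater, then an approach of multiple imputation based on" a cited standard method. It uses regression-based fully conditional specification with five data sets. The covariate list, worded alike in 8.7.1 to 8.7.3, starts with arm, age group, sex and BMI group and ends "race/ethnicity, material used in the TKA revision, and co-morbidities in the imputation model". SSC, re-operation, revision type, site and scores at other visits are not listed.

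Protocol 4.15 states: "Subjects who undergo a subsequent surgery involving the initial TKA incision within 90 days must withdraw from the study". Protocol 4.4.2 ends evaluations and data collection at withdrawal. KOOS and PROMIS are scheduled up to the Long Term Follow-up visit (day 90 to 104).

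Protocol 8.1.3.2 and 8.1.3.3 separate incomplete, discontinued and not-done assessments. SAP 10 replaces these with one class, worded for KOOS as "Missing assessment score for any reason" and almost identically for PROMIS. Protocol 8.3.6 provides for descriptive missing-data patterns and permits further imputation analyses without specifying them.

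**The concern.** A sensitivity analysis for missing data is useful when it relaxes the assumption the main analysis rests on. This one does not: both analyses treat a missing score as predictable from what the model contains, and neither contains SSC or re-operation.

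Here part of the missingness follows from the outcome by rule. The SSC definition (Protocol 4.11.1.1) includes seroma or hematoma requiring surgery and necrosis requiring excision or re-operation, so some subjects with severe SSCs will have surgery through the incision and leave. Their later scores are then filled in, explicitly or implicitly, as if they resembled subjects of the same arm and baseline profile, most of whom had no SSC. If SSCs are commoner under standard of care (SOC), more poor scores are removed from that arm and the difference shrinks. Two analyses sharing this bias can agree, and the agreement would be read as reassurance.

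**Working it through.** **The plan's own figures.** The documents give no figure for missing questionnaire scores. The nearest is SAP 2.1: "at least 80% power to detect a difference of 10% (50% reduction) in SSCs in the ciNPT arm with 199 subjects in each treatment arm", and "With an estimated 5%-10% loss" a total of 440. A two-proportion calculation (20% v 10%, two-sided 0.05) reproduces 199 per arm with 80.0% power. Loss from 440 to 398 is 42/440 = 9.5%.

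**Inputs.** SSC rate p = 0.20 in SOC and 0.10 in ciNPT (SAP 2.1). Not in the documents: the share w of SSC subjects who leave before Day 90, taken as equal in both arms; other loss of 5% or 10%, unrelated to SSC; and a 15-point lower Day 90 KOOS after an SSC. The target is taken as the mean score of all randomised subjects, since SAP 8.7 uses the ITT set.

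**Loss by arm.** The rule removes a share pw: at w = 25%, 5.0% of SOC and 2.5% of ciNPT; at w = 50%, 10% and 5%. SOC loses twice as many.

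**Attenuation.** If the listed covariates do not predict SSC within arm, the imputed mean equals the observed mean. The SSC share among observed subjects is p(1−w)/(1−pw). At w = 50%: SOC 0.10/0.90 = 11.1%; ciNPT 0.05/0.95 = 5.3%; difference 5.85 points instead of 10. Multiplied by 15, this is 0.88 instead of 1.50.

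**Missing rate.** Averaged over arms it is 1 − (1 − 0.15w)(1 − other loss), because 0.15 is the mean SSC rate.

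| w | SSC share observed, SOC / ciNPT | Difference (true 1.50) | Lost | Day 90 missing, 5% other loss | 10% other loss |
|---|---|---|---|---|---|
| 10% | 18.4% / 9.1% | 1.39 | 7% | 6.4% | 11.4% |
| 25% | 15.8% / 7.7% | 1.21 | 19% | 8.6% | 13.4% |
| 50% | 11.1% / 5.3% | 0.88 | 42% | 12.1% | 16.8% |
| 75% | 5.9% / 2.7% | 0.48 | 68% | 15.7% | 20.1% |

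The percentage lost does not depend on the 15 points.

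**Does the check reveal it?** A large-sample simulation (200,000 per arm) compared the listed imputation with a missing-at-random likelihood model standing in for the mixed model. All settings are assumptions: w = 25% or 50%, 7.5% other loss, SD 18, between-visit correlation 0.6, a 10-point deficit after an SSC without re-operation, and 10, 20 or 30 points with it.

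- The true difference was 0.95 to 2.06 points. The listed imputation gave 0.53 to 0.96 and the likelihood model 0.54 to 1.05.
- When re-operation left no signal in the End of Treatment score, the two agreed within 0.02 point, and both missed the truth by 0.2 to 1.4 points.
- When it left an early signal, they differed by 0.05 to 0.44 point, and the imputation was further from the truth.
- Adding SSC status gave 0.92 to 1.14. This sufficed only when re-operated subjects scored like other SSC subjects; otherwise 0.24 to 1.03 points of bias remained.
- A correctly sized delta shift for re-operated subjects, on top of SSC status, came within 0.1 point of the truth.

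**The case against.** Several stronger readings are tempting, and the documents do not support them.

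*The check would usually not run, because planned loss is 5% to 10%.* That loss concerns evaluability for the SSC endpoint. A subject with an SSC who then withdraws counts as an event and stays in the mITT set (Protocol 8.1.1, 8.2), so score missingness comes on top. With 9.5% other loss, Day 90 missingness is 1 − 0.9625 × 0.905 = 12.9% at w = 25% and 1 − 0.925 × 0.905 = 16.3% at w = 50%. Any single KOOS subscale can also trigger the rule. Whether it runs depends on the assumptions.

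*Pain is affected in the same way.* SAP 4.3.1 ends pain scoring at End of Treatment. Only withdrawal before that assessment could remove a score, so the route is small.

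*The informative part cannot be separated.* Discontinuation reasons are recorded (Protocol 4.16) and tabulated (SAP 8.1), and SAP 10 does not withdraw the missing-data patterns of Protocol 8.3.6. What is lacking is a specified table by score, arm and visit.

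*Most SSC subjects are lost.* Withdrawal applies to further surgery through the incision or a repeat revision. Other SSC subjects stay in follow-up (Protocol 4.11.1), and nothing in the documents supports a share as high as 50% or 75%.

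Three further objections have weight. The SAP calls its imputation text a basic description, and the method would ordinarily also use scores at other visits. In a separate simulation at w = 50% (220 per arm, SD 20, correlation 0.5) that reading recovered 1.00 of 1.50 points, against 0.84 for the listed covariates: better, but still short. Second, the bias is small against noise: the standard error of the difference is √(2 × 20²/220) = 1.9 points, against a bias of 0.29 to 0.62 point at w = 25% to 50%. Third, under the planned rates the bias is toward no difference, so it would not create a false claim of benefit.

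**Conclusion.** The point holds for KOOS and PROMIS. The imputation and the mixed model share the missing-at-random assumption, neither contains SSC or re-operation, and the protocol makes later scores missing by rule after further surgery through the incision. Agreement between them would not show absence of bias. Below 10% missing the SAP specifies no check, and it does not define the rate by visit or arm.

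The size rests on three assumptions: the planned 20% v 10% SSC rates hold, the same share of SSC subjects leaves in each arm, and that share is 25% to 50%. About 19% to 42% of the SSC-mediated score difference is then lost; at a 10% share it is about 7%. If the SSC rates do not differ as planned, the direction is not assured.

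This is a cheap improvement to exploratory analyses. The primary analysis and the sample size are unaffected.

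**What to change.** In SAP 8.7.2 and 8.7.3:

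1. Add to the imputation model SSC occurrence before the visit, withdrawal for subsequent surgery, revision type, site and scores at other visits.
2. Run the sensitivity analysis whatever the overall missing rate.
3. Add one delta-adjusted (tipping-point) imputation for subjects withdrawn for subsequent surgery or after an SSC. Item 1 alone does not remove the bias if they fare worse than other SSC subjects.
4. Report the protocol's missingness categories by arm and visit, as Protocol 8.1.3.2, 8.1.3.3 and 8.3.6 provide.

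SSC onset dates, interventions and discontinuation reasons are already collected, so the cost is SAP wording and some programming. The downside is a few more exploratory tables and the need to choose and justify a delta range before database lock.

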8.7.3 PROMIS Global 10 t-score Analysis

For calculation purpose, the PROMIS Adult Global Scale v1.2 will be followed and used for this study.

Global07 has a scale of 0 (0 indicating no pain) to 10 (indicating worst pain imaginable) response scores. Global01, Global10, Global08, Global06, Global02-05, and Global09 will be asked on a 5-point Likert scale and their numeric values as listed below:

Value	5	4	3	2	1
Global01	Excellent	Very Good	Good	Fair	Poor
Global10	Never	Rarely	Sometimes	Often	Always
Global08	None	Mild	Moderate	Severe	Very Severe
Global06	Completely	Mostly	Moderately	A Little	Not At All
Global09, 05, 04, 03, 02	Excellent	Very Good	Good	Fair	Poor
Global07	0	1-3	4-6	7-9	10

The 10-question PROMIS Global-10 has 2 subscales:

Global Physical Health raw score = (Global03+ Global06 + Global07 + Global08)

Global Mental Health raw score = (Global02 + Global04 + Global05 +Global10)

All four questions in each subscale must be answered in order to produce a valid raw score. The raw score will be converted into T-Score according to the conversion table below.

Global Physical Health Conversion Table			Global Mental Health Conversion Table		
Raw Score	T Score	Standard Error	Raw Score	T Score	Standard Error
4	16.2	4.8	4	21.2	4.6
5	19.9	4.7	5	25.1	4.1
6	23.5	4.5	6	28.4	3.9
7	26.7	4.3	7	31.3	3.7
8	29.6	4.2	8	33.8	3.7
9	32.4	4.2	9	36.3	3.7
10	34.9	4.1	10	38.8	3.6
11	37.4	4.1	11	41.1	3.6
12	39.8	4.1	12	43.5	3.6
13	42.3	4.2	13	45.8	3.6
14	44.9	4.3	14	48.3	3.7
15	47.7	4.4	15	50.8	3.7
16	50.8	4.6	16	53.3	3.7

17	54.1	4.7		17	56.0	3.8
18	57.7	4.9		18	59.0	3.9
19	61.9	5.2		19	62.5	4.2
20	67.7	5.9		20	67.6	5.3

The range of a T-Score for Global Physical Health will be from 16.2 to 67.7 with higher scores reflecting better health. The range of a T-Score for Global Mental Health will be from 21.2 to 67.6 with higher scores reflecting better health. For both Global Physical Health and Global Mental Health, a positive value of change from baseline indicates improved health post-baseline as compared with baseline; a negative value indicates declined health post-baseline as compared with baseline.

Both Global Physical Health and Global Mental Health T-Scores and their corresponding changes from baseline will be summarized separately by treatment arm and by visit. Changes from baseline for both Global Physical Health and Global Mental Health T-Scores will be analyzed separately using a mixed model, which includes (“Treatment Arm” and “Visit”) plus the interaction term (“Treatment Arm by Visit”), revision type, clinical site, and with subject as a random effect. LS means along with 95% confidence intervals and p-values at each post-baseline timepoint will be presented.

If a missing data rate for Global Physical Health or Global Mental Health is 10% or greater, then an approach of multiple imputation based on Rubin’s [1976, 1987]^{3,4} for missing data for both Global Physical Health and Global Mental Health will be used by creating several different plausible imputed data sets and appropriately combining results obtained from each of them. A basic description of the multiple imputation includes:

1. Using SAS procedures including Proc MI and Proc MIANALYZE;
2. Using the fully conditional specification (FCS) method / algorithm [Brand 1999 and van Buuren 2007]^{5,6} which is a linear regression for continuous variables;
3. Including treatment arm, age (≥ 65 or < 65 years), sex, BMI (≥ 35 kg/m² or < 35 kg/m²), race/ethnicity, material used in the TKA revision, and co-morbidities in the imputation model;
4. Creating five imputed datasets [Rubin 1996]⁷;
5. Combining completed-data estimates from five imputed datasets.

The mixed model analysis for both Global Physical Health and Global Mental Health described above will be repeated based on the imputed data.

8.7.4 30-Day Subject Incidence of SSC Analysis

The proportion of subjects with each value of “Occurred” or “No occurrences” or “Incomplete-Follow-up” for 30-Day SSC will be summarized, as applicable, by treatment arm based on the ITT, mITT analysis sets. Additionally, 30-Day SSC events by type: superficial SSI, deep SSI, dehiscence, seroma, hematoma, skin necrosis, or continued drainage will be summarized based on the mITT analysis set.

Superiority Testing

The following hypothesis will be tested for superiority:

Null H_0 : $\Delta_{\text{ciNPT-SOC}} = 0$

Alternative H_a : $\Delta_{\text{ciNPT-SOC}} \neq 0$

where $\Delta_{\text{ciNPT-SOC}}$ is the difference in the proportion of subjects in the ciNPT arm with at least one SSC and the proportion of subjects in the SOC dressing arm with at least one SSC.

For the combined population, a Cochran-Mantel-Haenszel (CMH) test stratified by type of revision (Septic, Aseptic) will be used to compare the SSC incidence rates between two treatment arms based on the mITT analysis set. The odds ratio and its asymptotic 95% confidence interval will be computed. This test is equivalent to the test of difference for the proportions.

For the septic and aseptic subpopulations, a Chi-square or Fisher's test, as appropriate will be performed within each revision type for SSC incidence rates between treatment arms based on the corresponding mITT analysis set.

Additionally, figure(s) may be generated to display the results from the analyses of this endpoint graphically.

8.7.5 45-Day Subject Incidence of SSC Analysis

Any 45-Day subject incidence of SSC will be analyzed in a similar fashion as the 30-Day subject incidence of SSC endpoint described in section 8.7.4 of this document.

8.7.6 Time to SSC Analysis

Time to SSC: defined as the time in day(s) from the date of TKA revision to the first SSC event and is calculated as:

$TTSSC = (\text{Start Date of the first SSC} - \text{Date of the TKA revision}) + 1$

Censoring will occur for the following:

- 1.) Subjects who experience their first SSC on the day of TKA revision after initial dressing application will be considered to have a time to SSC of 1 day.
- 2.) Subjects, who do not have any SSC assessment after initial dressing application and they withdraw before the first scheduled SSC assessment at the end of treatment, will be censored at the date of TKA revision.
- 3.) Subjects who do not have any SSC assessment at Day 90 will be censored at Day 90 or end of study date, whichever comes first.

A Kaplan-Meier curve will be generated for each treatment arm and the quartile estimates will be generated as well. A log-rank test will be used to compare the time-to-SSC between treatment arms. These analyses may be repeated utilizing data calculated from the additional way of calculation described above.

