2.4 Randomization

Subjects who meet all inclusion criteria and no exclusion criteria will be randomized in a 1:1 ratio to either the ciNPT or SOC dressing treatment arm. The randomization will be stratified by status at revision (septic versus aseptic).

For each stratum, a randomization schedule including randomization numbers and treatment assignments will be generated and maintained centrally in the web-based clinical database management system. Once randomized, a subject's assignment cannot be altered or changed; a subject should not be randomized twice.

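### The log-rank test for time to SSC in SAP 8.7.6 omits the septic/aseptic randomisation stratum, at a cost of about 2 to 3 points of power at the planned effect

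*SAP*

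**What the plan says.** SAP 8.7.6 defines time to SSC from the date of the TKA revision, gives censoring rules, and plans Kaplan-Meier curves by arm with quartile estimates. The comparison is one sentence: "A log-rank test will be used to compare the time-to-SSC between treatment arms". No stratum, covariate or hazard ratio is named.

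On allocation, SAP 2.4 makes septic or aseptic status the stratification factor. Subjects "will be randomized in a 1:1 ratio to either the ciNPT or SOC dressing treatment arm", and "For each stratum, a randomization schedule including randomization numbers and treatment assignments will be generated and maintained centrally". No block size is given there or in Protocol 8.4.3.

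On expected event rates, SAP 2.1 states that "the assumed SSC rate is 33% for septic and 6.9% for aseptic", and adds: "This study plans to enroll at least 50% septic revisions overall".

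The neighbouring analyses do use revision type:
- SAP 8.5 (primary): CMH test stratified by randomised revision type.
- SAP 8.6.1 and 8.6.2 (any SSI, deep SSI): CMH test stratified by randomised and actual type.
- SAP 8.7.4 and 8.7.5 (30-day and 45-day SSC): CMH test stratified by revision type.
- SAP 8.7.1 to 8.7.3 (pain, KOOS, PROMIS): mixed models that include revision type.

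The opening of SAP 8.7 says that exploratory analyses which include revision type use the actual type. It does not say that every analysis must include it. The version 2.0 changes in SAP 10 revise the censoring in 8.7.6 and add no stratum.

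**The concern.** Revision type is expected to be strongly prognostic: 33/6.9 = 4.78, nearly a fivefold difference in risk. A test that pools the two strata loses some power. If allocation is also balanced within each stratum, the pooled variance contains a between-stratum part that the design has already removed from the comparison of arms, so the test rejects less often than its nominal level.

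What is at stake is modest. By the default in SAP 8.7, time to SSC is analysed on the ITT set, and through censoring it uses subjects with incomplete follow-up whom the primary mITT analysis excludes. It is therefore a natural companion to the primary test. It is better if the two differ only in how they treat follow-up, and not also in whether they stratify.

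**Working it through.** **Inputs from the documents.** SSC rates of 33% (septic) and 6.9% (aseptic), at least 50% septic, 20% against 10% overall, 199 evaluable per arm, 440 randomised, 5% to 10% loss, two-sided 0.05 (SAP 2.1); 1:1 allocation with one schedule per stratum (SAP 2.4); 90-day follow-up (SAP 8.7.6).

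**Assumed, because not given.** Event-time shape (exponential, and Weibull with shape 0.5), block size (exact balance, 4, 6, or unblocked), the same relative reduction in both strata, and 7.5% random dropout.

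**1. The plan's own figure.** No sample size or power is stated for the log-rank test, so the check is on the primary calculation.
- Pooled rate: (0.33 + 0.069)/2 = 0.1995, which agrees with the stated 20%.
- Two-proportion formula: n = [1.96·√(2·0.15·0.85) + 0.8416·√(0.2·0.8 + 0.1·0.9)]² / 0.10² = (0.990 + 0.421)²/0.01 ≈ 199 per arm.
- Likelihood-ratio version: 196.9 × 1.0078 (O'Brien-Fleming inflation) = 198.4, so 199.

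The stated 199 is reproduced, and the planning rates can be carried forward.

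**2. Analytic size under balance within strata.** With no treatment effect and equal strata, the ratio of within-stratum to total variance is

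[(0.33·0.67 + 0.069·0.931)/2] / (0.1995·0.8005) = 0.1427/0.1597 = 0.893.

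The unstratified statistic then has standard deviation √0.893 = 0.945. The 1.96 cut-off acts like 1.96/0.945 = 2.07, which gives a two-sided size of about 3.8%.

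**3. Simulation.** 440 subjects, 50% septic, censoring at 90 days, 7.5% dropout, both tests on the same data, nominal two-sided 5%:

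| Allocation within stratum | Scenario | Unstratified | Stratified |
|---|---|---|---|
| Blocks of 4 | No effect (size) | 0.038 | 0.050 |
| Blocks of 6 | No effect (size) | 0.039 | 0.051 |
| Unblocked | No effect (size) | 0.049 | 0.050 |
| Blocks of 4 | 50% reduction (power) | 0.843 | 0.862 |
| Blocks of 6 | 50% reduction (power) | 0.840 | 0.861 |
| Unblocked | 50% reduction (power) | 0.832 | 0.859 |
| Blocks of 4 | 40% reduction (power) | 0.625 | 0.661 |

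**4. Sensitivity.**
- Repeat runs with balanced strata at 50% septic put the size of the unstratified test between 0.034 and 0.039.
- For septic shares of 40% to 75% its size is 3.6% to 4.3%.
- At a 50% reduction the power loss over all scenarios is 0.6 to 2.8 points, smallest at 75% septic.
- With 199 per arm, power is 0.80 against 0.82.
- Weibull event times change little.
- With the same 20% rate in both strata, both tests have size 0.050, so the omitted stratum is the cause.

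**The case against.** The strongest reply is that nothing depends on this test. Time to SSC is not in the exploratory endpoint lists of Protocol 3.6 or SAP 4.3. It appears only among the analyses in SAP 8.7, with no alpha or power target. An unstratified log-rank test is valid and matches the by-arm Kaplan-Meier curves, and any error in size is towards caution. All of this stands, and it makes the point minor. It does not make the unstratified test the better choice, since the stratum is known for every subject and already used in the other SSC tests.

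The SAP is also silent on stratification and does not exclude it. That is true, but beside sections that name revision type each time, a plain log-rank test reads as unstratified.

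A reader might infer four stronger things that the documents do not support:

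- **That the test is conservative whatever the allocation.** This needs balance within strata. With one schedule per stratum and no stated block size, unblocked 1:1 allocation is possible, and size is then nominal. Only the power loss survives both cases.
- **That this is the only SSC comparison using partial follow-up.** SAP 8.5.1 lists an optional stratified CMH test on the ITT set, which contains subjects with incomplete follow-up. How their status would be counted is not stated, so uniqueness is not established.
- **That the missing stratum would drive disagreement with the primary test.** Under exact balance, the unstratified log-rank and the mITT CMH test differ on significance in 2.6% of simulated trials at a 50% reduction, against 2.3% for the stratified log-rank (4.6% and 4.1% at a 40% reduction). Most disagreement comes from the different test and analysis set. With unblocked allocation the gap is wider, 5.9% against 2.4%, but the loss of size is then absent.
- **That every p-value will be too large.** With exact balance and no effect, the unstratified p-value was the smaller of the two in 32% of trials.

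**Conclusion.** The point holds as a minor one. As written, SAP 8.7.6 leaves out the factor used to stratify randomisation, unlike the other planned SSC tests of the combined population. At the planning rates this costs about 2 to 3 points of power at a 50% reduction and 3 to 4 points at a 40% reduction. These figures assume a septic share near 50% and a common relative effect, and the loss shrinks as the septic share rises. Mild conservatism, about 3.4% to 3.9% at nominal 5%, comes in addition only if allocation is balanced within strata. The omission does not raise the false-positive risk and does not touch the primary conclusion.

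**What to change.** In SAP 8.7.6, specify a log-rank test stratified by revision type. Preferably add a hazard ratio with 95% CI from a Cox model stratified the same way. The estimate is useful because, at pooled 90-day rates of 20% and 10%, neither Kaplan-Meier curve is expected to fall to 75%, so the planned quartiles may not be estimable.

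The new sentence must say which revision type is used. Randomised type matches the primary CMH test in SAP 8.5 but conflicts with the rule at the head of SAP 8.7. If it is chosen, write it as an explicit exception to that rule and give actual type as a sensitivity analysis. The unstratified test can be kept as a further sensitivity analysis.

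The cost is one or two SAP sentences before database lock and one strata term in the program. No new data are needed, and the design and the primary analysis do not change.
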